7.8.1.2 Secondary Analysis

Analysis Set: Per Protocol Set

Analysis

Variable(s): Proportion of subjects with a maximum NRS score of 1 or less during the 28 days before the final dose of study drug

Analytical

Method(s): An analysis similar to the above “Primary analysis” will be performed using the PPS to assess the robustness of the results.

7.8.1.3 Examination of Subgroups

Analysis Set: Full Analysis Set

Analysis

Variable(s): Proportion of subjects with a maximum NRS score of 1 or less during the 28 days before the final dose of study drug

Subgroup(s):	Age (years)	[20<= - <30, 30<= - <40, 40<= - <50, 50<= - <=Max]
	BMI (kg/m ²) at Baseline	[Min<= - <18.5, 18.5<= - <25.0, 25.0<= - <=Max]
	Birth Experience	[Yes, No]
	Volume of Uterus at Baseline (cm ³)	[Min<= - <=28, 28< - <=170, 170< - <=700, 700< - <=Max]
	Maximum NRS Score at Baseline	[4<= - <7, 7<= - <=Max]
	Type of Uterine Fibroid	
	Subserosal Fibroid	[Yes, No]
	Intramural Fibroid	[Yes, No]

Analytical

Method(s): (1) Descriptive Statistics

The point estimate and 2-sided 95% exact confidence interval of the proportion of subjects with a maximum NRS score of 1 or less during the 28 days before the final dose of study drug will be summarized for above each subgroup by treatment group.

7.8.2 Secondary Efficacy Endpoint(s)

7.8.2.1 NRS Score

Analysis Set: Full Analysis Set

Analysis

Variable(s): Proportion of subjects with a maximum NRS score of 0 during the 28 days before the final dose of study drug

Mean NRS score during the 28 days before the final dose of study drug

Number of days without pain symptoms (NRS = 0) during the 28 days before the final dose of study drug

Analytical

Method(s):

- (1) Proportion of subjects with a maximum NRS score of 0 during the 28 days before the final dose of study drug will be summarized by treatment group. The point estimate and 2-sided 95% confidence interval of odds ratio will be calculated between TAK-385 40 mg group and placebo group (TAK-385 40 mg group / placebo group).
- (2) For mean NRS score and number of days without pain symptoms (NRS = 0), descriptive statistics will be provided for the observed values and the change from baseline by treatment group. The mean differences between TAK-385 40 mg group and placebo group and the two-sided 95% confidence intervals will be provided.

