9.1.17 Pain Symptoms, Other Clinical Symptoms, and QOL

Pain symptoms are evaluated using the NRS score. The investigator or subinvestigator distributes the patient diary to consented subjects. Subjects fill out the patient diary every day from VISIT 1 to the day before VISIT 6 (or until early termination). Subjects record pain symptoms within 24 hours associated with uterine fibroids (NRS score), menstruation, and use of analgesics. If subjects use any analgesics for pain associated with uterine fibroids, they should record this fact in the patient diary along with the accompanying pain symptoms before use of analgesics. The start/end date of menstruation must be recorded in CRF in reference to the patient diary by the investigator or subinvestigator. If there is anything unclear or insufficient description in the patient diary, queries may be made to the subject, and corrections to the patient diary are recorded by the subject in a change history that captures the old information, the new information, identification of the person making the correction and the date of the correction. If it is impossible to make queries to the subject at site visits, queries will be made to the subject with telephone calls or other means, and corrections to the patient diary are recorded by the investigator or subinvestigator in a change history that captures the old information, the new information, identification of the person making the correction and the date of the correction.

The uterine fibroid symptom and QOL (UFS-QOL) score is used to evaluate other clinical symptoms and the QOL of subjects. The investigator or subinvestigator distributes the UFS-QOL questionnaire at VISITS 3 and 6, and has subjects fill it out before physical examination at site visit.

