7.0 METHODS OF ANALYSIS AND PRESENTATION

7.1 General Principles

All statistical analyses will be conducted using SAS® Version 9.2, or higher.

A statistical test for the primary endpoint will be reported as 2-sided and will be assessed at $\alpha=0.05$ significance level and all confidence intervals will be reported as 2-sided unless otherwise stated. P-values will be rounded to 4 decimal places prior to assessment of statistical significance.

Means and medians will be presented to 1 more decimal place than the recorded data. The standard deviations (SDs) will be presented to 2 more decimal places than the recorded data. Confidence intervals about a parameter estimate will be presented using the same number of decimal places as the parameter estimate.

Where appropriate, variables will be summarized descriptively by study visit. For the categorical variables, the count and proportions of each possible value will be tabulated by treatment group. The denominator for the proportion will be based on the number of subjects who provided non-missing responses to the categorical variable. For continuous variables, the number of subjects with non-missing values, mean, median, SD, minimum, and maximum values will be tabulated. Confidence intervals for continuous variables will be calculated based on t-statistics and ones for categorical variables will be based on Wald confidence intervals without using any model, unless otherwise stated.

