7.1.1 Study Definitions

Duration of exposure to double-blind study drug (days):

Date of last dose of double-blind study drug - date of first dose of double-blind study drug +
1

Double-blind study drug compliance (%):

Number of double-blind study drugs taken/duration of exposure to double-blind study drug*
100 (rounded to 1 decimal places)

Disease Duration (years):

((year of informed consent*12 + month of informed consent) -(year of first defined diagnosis of uterine fibroids*12 + month of first defined diagnosis of uterine fibroids))/12 (rounded to 1 decimal places)

Maximum Drug Holidays (days):

Maximum number of consecutive days on which the subject does not take the study drug for the treatment period

Proportion of subjects with a maximum NRS score of 1 or less during the 28 days before the final dose of study drug

CONFIDENTIAL

((number of subjects with a maximum NRS score of 1 or less during the last 28 days of the treatment)/(number of subjects with available data during the 27 days before the final dose of study drug and the date))*100 (rounded to 1 decimal places)

Similarly, for proportion of subjects with a maximum NRS score of 0 during the 27 days before the final dose of study drug and the date, its numerator will be defined as number of subjects with a maximum NRS score of 0 during the 27 days before the final dose of study drug and the date.

Number of days without pain symptoms (NRS = 0) during the 28 days before the final dose of study drug (%):

((number of days without pain symptoms (NRS = 0) during the last 28 days of the treatment)/(number of days with available data during the last 28 days of the treatment))*100 (rounded to 1 decimal places)

Maximum NRS score at baseline

Maximum NRS score from first day of menstrual period confirmed at Visit 2 to a day prior to menstrual period confirmed at Visit 3

Mean NRS score at baseline

Mean NRS score from first day of menstrual period confirmed at Visit 2 to a day prior to menstrual period confirmed at Visit 3

Maximum NRS score from Day 1 to 28, 29 to 56, and 57 to 84

Maximum NRS score from Day 1 to earlier of Day 28 or Follow-up Day 3.

Similarly, Maximum NRS score from Day 29 to 56 and from Day 57 to 84 will be defined as maximum NRS score from Day 29 to earlier of Day 56 or Follow-up Day 3 and from Day 57 to earlier of Day 84 or Follow-up Day 3, respectively.

Mean NRS score from Day 1 to 28, 29 to 56, and 57 to 84

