7.1.4 Methods for Handling Missing Data

All available efficacy and safety data will be included in data listing and tabulations. No imputation of values for missing data will be performed unless otherwise specified.

- For UFS-QoL, published scoring manuals and guidelines will be used to calculate UFS-QoL and handle missing data (see Appendix 3).
- For myoma or uterus volume, if D1 and D2 of the myoma or uterus are present but D3 is missing, then the volume will be calculated as $D1*D2*D2*\pi/6$ (cm^3).
- For LH, FSH, E₂, P and clinical laboratory tests, values less than the lower limit of quantification will be treated as zero when calculating the descriptive statistics.

- Disease duration with first diagnosis date of uterine fibroid that are completely or partially missing will be derived as follows:
 1. If the year is missing, then the disease duration will be treated as missing.
 2. If the year is present but the month is missing, then the month will be treated as January for the calculation.

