7.8.2.2 NRS Score time course

Analysis Set: Full Analysis Set

Analysis

Variable(s): Proportion of subjects with a maximum NRS score of 1 or less

Proportion of subjects with a maximum NRS score of 0

Mean NRS score

Number of days without pain symptoms (NRS = 0)

Visit: Baseline, Day 1 to 28, Day 29 to 56, Day 57 to 84

Analytical Summaries (1) and (2) will be provided by each visit.

Method(s):

- (1) Proportion of subjects with a maximum NRS score of 1 or less and proportion of subjects with a maximum NRS score of 0 will be summarized by treatment group. The point estimate and 2-sided 95% confidence interval of odds ratio will be calculated between TAK-385 40 mg group and placebo group (TAK-385 40 mg group / placebo group).
- (2) For mean NRS score and number of days without pain symptoms (NRS = 0), descriptive statistics will be provided for the observed values and the change from baseline by treatment group. The mean differences between TAK-385 40 mg group and placebo group and the two-sided 95% confidence intervals will be provided.

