7.8.3 Additional Efficacy Endpoint(s)

7.8.3.1 Myoma Volumes and Uterine Volumes

Analysis Set: Full Analysis Set

Analysis

Variable(s): Myoma volumes
Uterine volumes

Visit: Baseline , Week 12

Analytical

Method(s): For each variable, descriptive statistics will be provided for the observed values and the percent changes from baseline by treatment group. The mean differences in the percent changes from baseline between TAK-385 40 mg group and placebo group and the two-sided 95% confidence intervals will be provided.

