7.8.3.3 UFS-QOL Score

Analysis Set: Full Analysis Set

Analysis

Variable(s): Symptom Severity
Concern
Activities
Energy/Mood
Control
Self-consciousness

Visit: Sexual Function
Visit: HRQL Total
Visit: Baseline , Week 12
Analytical
Method(s): For each variable, descriptive statistics will be provided for the observed values and the changes from baseline by treatment group.
The mean differences in the observed values between TAK-385 40 mg group and placebo group and the two-sided 95% confidence intervals will be provided.

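### Mean NRS, pain-free days and UFS-QOL are compared by unadjusted mean differences, with no scale named for the two NRS endpoints; adjusting for the baseline already collected would usually narrow these valid intervals at almost no cost

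*SAP*

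**What the plan says.** For mean NRS score and pain-free days over the last 28 days of treatment, SAP 7.8.2.1 item (2) summarizes both observed values and changes from baseline by arm, then adds: "The mean differences between TAK-385 40 mg group and placebo group and the two-sided 95% confidence intervals will be provided". It does not say which of the two is differenced. SAP 7.8.2.2 uses the same text for the time course, where "Summaries (1) and (2) will be provided by each visit" and Baseline is one of the listed visits.

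Neighbouring sections do name a scale. For fibroid and uterine volumes (7.8.3.1) it is "The mean differences in the percent changes from baseline between TAK-385 40 mg group and placebo group". For UFS-QOL (7.8.3.3): "The mean differences in the observed values between TAK-385 40 mg group and placebo group and the two-sided 95% confidence intervals will be provided"; UFS-QOL changes from baseline are only described by arm.

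SAP 7.1 sets the method: "Confidence intervals for continuous variables will be calculated based on t-statistics". No baseline-adjusted estimate appears in either document as available.

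The baseline data are there. SAP 7.1.1 defines baseline mean NRS as "Mean NRS score from first day of menstrual period confirmed at Visit 2 to a day prior to menstrual period confirmed at Visit 3". Under Protocol 9.1.17 the investigator "distributes the UFS-QOL questionnaire at VISITS 3 and 6", and the diary is kept daily from VISIT 1. SAP 7.1.1 gives no baseline formula for pain-free days.

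**The concern.** There are two specification gaps and one loss of precision.

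- **Scale.** For the two NRS endpoints the differenced quantity is not written down. Observed-value and change-score intervals from the same data differ in width, and a chance baseline imbalance moves the two estimates in opposite directions.
- **Pain-free days at baseline.** The change from baseline is required but cannot be derived from 7.1.1 as written. The endpoint is named as a number of days but calculated as a percentage of days with data. The run-in cycle may last 25 to 38 days (Protocol 7.1.3), against 28 days on treatment, so a count and a percentage would give different changes.
- **Precision.** These intervals are the only between-arm inference for the two continuous secondary efficacy endpoints. Arms are small (32 each), and Protocol 8.3 describes no stratification factor. An unadjusted difference leaves the baseline information unused.

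The planned intervals are unbiased over randomization. The primary test, its power and the primary conclusion are not at stake.

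**Working it through.** **Plan's own figure.** The sample size (SAP 6.0) concerns only the primary endpoint: 28 per group, 20.0% vs 65.0%, two-sided 5% Fisher's exact test, power above 90%. Exact enumeration gives 90.4%, so it reproduces. Nothing below changes it.

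**Inputs.** n = 32 per arm and 1:1 allocation come from the documents. They give no SD and no baseline-outcome correlation ρ, so both are assumed. Widths are in SD units with equal baseline and follow-up SDs.

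**Expected 95% half-widths** (N = 64; t(62) = 1.9990, t(61) = 1.9996; √(2/32) = 0.25):

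- Observed values: t(62) × 0.25 = 0.500.
- Change from baseline: 0.500 × √(2(1−ρ)).
- ANCOVA: t(61) × 0.25 × √(1−ρ²) × √(1+1/60). The last factor is the average cost of chance baseline imbalance.

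| ρ | Observed | Change | ANCOVA | ANCOVA/observed | ANCOVA/change |
|---|---|---|---|---|---|
| 0 | 0.500 | 0.707 | 0.504 | 1.009 | 0.713 |
| 0.2 | 0.500 | 0.632 | 0.494 | 0.988 | 0.781 |
| 0.3 | 0.500 | 0.591 | 0.481 | 0.962 | 0.813 |
| 0.5 | 0.500 | 0.500 | 0.437 | 0.873 | 0.873 |
| 0.7 | 0.500 | 0.387 | 0.360 | 0.720 | 0.930 |

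ANCOVA breaks even with observed values at ρ ≈ 0.13 (0.14 at 28 per arm). In 5,000 simulated trials per value of ρ, it gave the narrower interval than observed values in 20%, 33%, 60%, 83% and 99% of trials at ρ = 0, 0.1, 0.2, 0.3 and 0.5.

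**Scale alone.** The change-score interval is √(2(1−ρ)) times the observed-value interval: √1.4 = 1.18 at ρ = 0.3 and √0.6 = 0.77 at ρ = 0.7.

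**Chance imbalance.** The baseline mean difference has SD √(2/32) = 0.25 baseline SD. An imbalance of d shifts the observed-value difference by ρd and the change difference by −(1−ρ)d. For d = 0.25, the shifts at ρ = 0.3, 0.5 and 0.7 are 0.075, 0.125 and 0.175 SD for observed values, and 0.175, 0.125 and 0.075 SD the other way for changes.

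**Active arm near zero pain.** In phase 2, 75.9% of the 40 mg arm had a maximum NRS of 1 or less (SAP 6.0), so a floor effect is plausible. Assume placebo SD 1; active SD 0.3 or 0.5 with active ρ of 0, 0.2 or 0.3; 20,000 trials per scenario; common-slope ANCOVA.

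| Placebo ρ | ANCOVA/observed | ANCOVA/change |
|---|---|---|
| 0.3 | 0.967-0.990 | 0.652-0.704 |
| 0.5 | 0.919-0.957 | 0.683-0.735 |
| 0.7 | 0.850-0.904 | 0.711-0.762 |

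Here the imbalance shift follows the average of the two arms' slopes. With placebo slope 0.5 and active slope 0 to 0.15 (0.5 × 0.3), the average is 0.25 to 0.325. A 0.25 SD imbalance then moves the observed-value difference by 0.25 × 0.25 = 0.06 to 0.25 × 0.325 = 0.08 placebo SD. It moves the change difference by 0.25 × 0.75 = 0.19 to 0.25 × 0.675 = 0.17 the other way.

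**Coverage.** With normal data, including the floor scenarios above, 95% intervals covered 94.4-95.3% (observed), 94.7-95.5% (change) and 94.6-95.3% (ANCOVA). With skewed data near the floor, observed-value and ANCOVA intervals both covered 92-94%, within about half a point of each other. In those data, relative to observed values, ANCOVA was level at placebo ρ = 0.15 and narrower by 2% at 0.27, 7% at 0.48 and 23% at 0.86; relative to change scores it was 24-37% narrower.

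**The case against.** The strongest reply is that this is a preference between valid methods for untested endpoints. Protocol 13.1.3 promises only descriptive statistics for mean NRS and pain-free days, and SAP 7.1 attaches a test only to the primary endpoint. The SAP's intervals already go beyond the protocol. The larger gains also come from the equal-SD case, which is unlikely for NRS here; under a floor effect the gain over observed values is a few percent. That stands, and the size of the gain should be stated accordingly.

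The scale can be read from context: the preceding sentence names observed values and changes, and the SAP restricts to one scale elsewhere when it wants to. Both is the likely reading, and a reader given both could bracket the adjusted point estimate. They would still not have its narrower interval, and the intention should be written.

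Normal-data coverage does not settle the matter for a bounded score and a percentage that may pile up at 100%. The skewed-data check answers most of this: coverage falls a little for both methods, not for ANCOVA alone.

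The addition is not nothing. Two NRS variables over the final 28 days and three periods give 8 estimates, and eight UFS-QOL scores bring the total to 16. UFS-QOL is not a listed endpoint, and its scale is already stated. These are fair limits on priority, but they do not remove the gain or the two specification gaps.

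**Conclusion.** The concern holds and should be acted on, as a cheap improvement in precision and specification rather than a correction of an invalid analysis.

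Against change scores the gain is clear: 7-19% narrower at ρ = 0.7 down to 0.3 with equal SDs, and 24-35% in the floor-effect scenarios. Against observed values it is 4%, 13% and 28% at ρ = 0.3, 0.5 and 0.7 with equal SDs. For the NRS outcomes under a floor effect it is probably only 1-8% (placebo ρ 0.3-0.5). The worst case is about 1% wider. All of this rests on assumed correlations and SDs, so the exact gain cannot be fixed in advance.

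The unnamed scale and the missing baseline formula for pain-free days do not depend on those assumptions. They should be settled before unblinding whatever view is taken of ANCOVA.

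**What to change.** 1. In SAP 7.8.2.1(2), 7.8.2.2(2) for the post-baseline periods, and 7.8.3.3 at Week 12, add: *The adjusted mean difference (TAK-385 40 mg minus placebo) and its two-sided 95% CI will be estimated by ANCOVA with treatment and the corresponding baseline value, in subjects with both values.*
2. In 7.8.2.1 and 7.8.2.2, state whether the unadjusted difference is of observed values, changes from baseline or both, and keep it as supportive.
3. In 7.1.1, define baseline pain-free days as the percentage of days with NRS = 0 over the same run-in cycle as baseline mean NRS, with days with available data as denominator.
4. Report how many subjects each adjusted estimate loses for lack of a baseline.

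The cost is SAP wording, one derived variable and one simple model per outcome, with no new data. One degree of freedom is spent (about 1% of width if baseline is uninformative). Because SAP 7.1.4 says "No imputation of values for missing data will be performed unless otherwise specified", a subject without a baseline UFS-QOL score drops out of the adjusted estimate only.

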7.8.2.2 NRS Score time course

Analysis Set: Full Analysis Set

Analysis

Variable(s): Proportion of subjects with a maximum NRS score of 1 or less

Proportion of subjects with a maximum NRS score of 0

Mean NRS score

Number of days without pain symptoms (NRS = 0)

Visit: Baseline, Day 1 to 28, Day 29 to 56, Day 57 to 84

Analytical Summaries (1) and (2) will be provided by each visit.

Method(s):

- (1) Proportion of subjects with a maximum NRS score of 1 or less and proportion of subjects with a maximum NRS score of 0 will be summarized by treatment group. The point estimate and 2-sided 95% confidence interval of odds ratio will be calculated between TAK-385 40 mg group and placebo group (TAK-385 40 mg group / placebo group).
- (2) For mean NRS score and number of days without pain symptoms (NRS = 0), descriptive statistics will be provided for the observed values and the change from baseline by treatment group. The mean differences between TAK-385 40 mg group and placebo group and the two-sided 95% confidence intervals will be provided.

7.8.3 Additional Efficacy Endpoint(s)

7.8.3.1 Myoma Volumes and Uterine Volumes

Analysis Set: Full Analysis Set

Analysis

Variable(s): Myoma volumes
Uterine volumes

Visit: Baseline , Week 12

Analytical

Method(s): For each variable, descriptive statistics will be provided for the observed values and the percent changes from baseline by treatment group. The mean differences in the percent changes from baseline between TAK-385 40 mg group and placebo group and the two-sided 95% confidence intervals will be provided.

7.8.3.2 Use of Analgesic Medications During the Treatment

Analysis Set: Full Analysis Set

Analysis

Variable(s): Use of analgesic medications during the 28 days before the final dose of study drug

Analytical Descriptive statistics will be provided by treatment group.

Method(s):

7.8.3.3 UFS-QOL Score

Analysis Set: Full Analysis Set

Analysis

Variable(s): Symptom Severity
Concern
Activities
Energy/Mood
Control
Self-consciousness

Visit: Sexual Function
Visit: HRQL Total
Visit: Baseline , Week 12
Analytical
Method(s): For each variable, descriptive statistics will be provided for the observed values and the changes from baseline by treatment group.
The mean differences in the observed values between TAK-385 40 mg group and placebo group and the two-sided 95% confidence intervals will be provided.

7.9 Pharmacokinetic/Pharmacodynamic Analysis

7.9.1 Pharmacokinetic Analysis

Not applicable

7.9.2 Pharmacodynamic Analysis

7.9.2.1 LH, FSH, E₂, and P

Analysis Set: Full Analysis Set

Analysis

Variable(s) : LH
FSH
E₂
P

Visit: Baseline , Week 4, 8, 12 and Follow-up

Analytical

Method(s) : For each variable, summaries (1) and (2) will be provided by treatment group.

- (1) Summary of each variable and Change from Baseline by Visit.
Descriptive statistics for observed values for each visit and changes from baseline will be provided.
- (2) Case Plots
Plots over time for each subject will be presented.

7.10 Other Outcomes

Not applicable

7.11 Safety Analysis

7.11.1 Adverse Events

7.11.1.1 Overview of Treatment-Emergent Adverse Events

Analysis Set: Safety Analysis Set

Analysis

Variable(s) : TEAE

Categories: Relationship to Study Drug [Related, Not Related]
Intensity [Mild, Moderate, Severe]

Analytical

Method(s) : The following summaries will be provided for each treatment group.

- (1) Overview of Treatment-Emergent Adverse Events
 - 1) All Treatment-Emergent Adverse Events (number of events, number and percentage of subjects)
 - 2) Relationship of Treatment-Emergent Adverse Events to study drug (number of events, number and percentage of subjects)
 - 3) Intensity of Treatment-Emergent Adverse Events (number of events, number and percentage of subjects)
 - 4) Treatment-Emergent Adverse Events leading to study drug discontinuation (number of events, number and percentage of subjects)
 - 5) Serious Treatment-Emergent Adverse Events (number of events, number and percentage of subjects)
 - 6) Relationship of serious Treatment-Emergent Adverse Events to study drug (number of events, number and percentage of subjects)
 - 7) Serious Treatment-Emergent Adverse Events leading to study drug discontinuation (number of events, number and percentage of subjects)
 - 8) Treatment-Emergent Adverse Events resulting in death (number

of events, number and percentage of subjects)
TEAEs will be counted according to the rules below.

Number of subjects

- Summaries for 2) and 6)
A subject with occurrences of TEAE in both categories (i.e., Related and Not Related) will be counted once in the Related category.
- Summary for 3)
A subject with multiple occurrences of TEAE will be counted once for the TEAE with the maximum intensity.
- Summaries other than 2) , 3) , and 6)
A subject with multiple occurrences of TEAE will be counted only once.

Number of events

For each summary, the total number of events will be calculated.

